14.1 Adverse events

All recorded adverse events will be coded according to the Medical Dictionary for Regulatory Activities (MedDRA). Treatment emergent adverse event (TEAE) is defined as an AE that begins or worsens in severity after at least one dose of study drug has been administered. Non-treatment emergent AEs are listed only.

TEAEs will be summarized using frequency and subject count tables. TEAEs will be tabulated by disease group, system organ class (SOC), preferred term (PT), causality and severity. For analysis purposes, each subject will also be categorized by the maximum severity reported for a given TEAE (similar PT) and these will be tabulated by maximum severity. If feasible, the AEs will be summarised by treatment cycles.

Serious adverse events (SAEs) and AEs leading to discontinuation will be summarized by disease group.

Pooled AE data from Part I and Part II will be tabulated by dose. Immune-mediated TEAEs will be listed. AE of special interest (AESI) will be listed.

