Part II of the trial will involve expansion groups of subjects by tumour type. The following tumour types will be selected for cohort expansion after the data of the first part of the trial has been reviewed: advanced hepatocellular carcinoma, cholangiocarcinoma and gallbladder cancer, pancreatic ductal adenocarcinoma, ovarian cancer, colorectal adenocarcinoma, cutaneous melanoma, uveal melanoma, gastric adenocarcinoma (including GE junction), ER+ breast cancer and anaplastic thyroid cancer. Each cohort will contain 10 subjects in Part II (10 at each dose level with random allocation within the same dosing schema Q3W, Q2W or Q1W. In addition, new dose level(s) 30 mg/kg and possibly also 45 and 100 mg/kg that include more than one tumour type will be tested for tolerability and safety. The data from both Part I and Part II will be used to define CLEVER-1 positivity in each tumour type. In Part III, subjects will be enrolled in tumour types that have demonstrated preliminary anti-tumour activity based on the CBR. Up to a total sample size of 700 subjects in all parts will be enrolled in approximately 20-30 sites in 5-8 countries. Subjects in Part III are stratified by disease type as in Part II and may be stratified by CLEVER-1 positivity. In Part II and Part III, cohorts for a particular tumour type may be opened sequentially or not opened at all i.e., if there is a strong signal for efficacy in cutaneous melanoma, that cohort may be opened first. Each cohort of subjects with a certain tumour type will be analysed for efficacy after 10 subjects have been treated with the dose(s) selected for Part II. The decision of continuing the cohort for Part III will be based on the results obtained from this analysis supported by the statistical rule to continue the cohort. Cohorts with best efficacy signal at any dose level may be advanced to Part III. However, it may not be meaningful to advance all Part II cohorts at any dose level with a minimal and clinically not meaningful signal of efficacy into Part III.

Figure 1A displays the trial pathway including dose escalation and expansion phases. **Figure 1B** displays how the initial design of the TITE-CRM will work in the absence of any DLT in Part I. Once a DLT is observed, subsequent dose decisions will be made with the usage of the TITE-CRM. This will take into account all accumulated DLT information—both partial (<9 weeks) and complete (9 weeks).

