11.3 Adverse Events

It is the responsibility of the Investigator to collect all AEs (both serious and non-serious) derived by observation, by spontaneous unsolicited reports of subjects, and, where appropriate, by routine open questioning.

As this is a first in human trial, all medical occurrences which meet the definition of an AE ([Section 5](#)) should be recorded. Disease progression will be recorded as an AE/SAE in this study.

Any **pre-existing conditions** or abnormal laboratory findings present at screening should be recorded in the medical history and should not be recorded as an AE unless the condition worsens by at least one CTC grade during the trial.

Abnormal laboratory findings (e.g., biochemistry, haematology, urinalysis) or other abnormal assessments (e.g., vital signs) that are judged by the Investigator as clinically significant will, if certain requirements are met, be recorded as AEs or SAEs. Clinically significant abnormal laboratory findings or other abnormal assessments that meet the definition of an AE or SAE and are detected during the study or are present at screening and significantly worsen following the start of the study, will be recorded as AEs or SAEs. However, clinically significant abnormal laboratory findings or other abnormal assessments that are associated with the disease being studied (unless judged by the Investigator as more severe than expected for the subject's condition), or that are present or detected at the start of the study and do not worsen, will not be recorded as AEs or SAEs. The Investigator will exercise their medical and scientific judgment in deciding whether an abnormal laboratory finding, or other abnormal assessment is clinically significant.

The Investigator should assess the seriousness and causality (relatedness to the study medication) of all AEs experienced by the subject and this should be documented in the source data. The trial site is responsible for providing full details of AEs/SAEs in the electronic data capture system in the designated eCRF forms continuously during the trial.

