- To assess the overall survival in trial subjects who receive at least 1 dose of FP-1305
- To measure cytokine and chemokine concentration in peripheral blood
- To measure the immune cell profile in circulation
- To assess if treatment elicits a change in LDH, LDL and oxLDL, CRP, CA-125 (OC subjects), CA19-9 (PDAC, gallbladder cancer, cholangiocarcinoma, gastric adenocarcinoma subjects), AFP (HCC subjects), CEA (CRC, ER+ BC, gastric adenocarcinoma subjects), CA-15-3 (ER+ BC subjects) levels or other relevant markers pre- and post-treatment

4 Design and type of the study

This is a prospective, three-part (see [Figure 1](#)) open label, Phase I/II dose-finding and separate cohorts expansion trial to determine the safety, tolerability and preliminary efficacy of repeated doses of CLEVER-1 antibody FP-1305 administered in three-weeks intervals (Q3W) in subjects with cutaneous melanoma, pancreatic ductal adenocarcinoma, ovarian cancer, colorectal adenocarcinoma, hepatocellular carcinoma, gallbladder cancer or cholangiocarcinoma, uveal melanoma, gastric (including GE junction) adenocarcinoma, ER+ breast cancer and anaplastic thyroid cancer.

In Part I 30 subjects were enrolled as planned. Part II consists of 10 enrolled subjects per cancer type (10 disease cohorts) at each selected Part II dose (1 mg/kg for all cohorts and 0.3 mg/kg, 1.0 mg/kg and 3.0 mg/kg for colorectal adenocarcinoma cohort) and dosing scheme (Q3W for all cancer types, Q2W and Q1W for selected cancer types). In addition to these, the study recruited cohorts for Q3W dosing of 3.0 mg and 10.0 mg for Cutaneous melanoma and Gastric adenocarcinoma, and also a cohort testing a higher dose (30.0 mg/kg) for any cancer cohort. Part III additional subjects will be enrolled based on the continuation rules set in the protocol (cohorts with at least 1/10 Clinical Benefit Rate will be expanded to total of 29 evaluable subjects). Thus, it is estimated that the total number of subjects in the whole trial can be up to 700 enrolled subjects.

In the study protocol, the study drug is set to be administered Q3W intervals. Based on the analysis of the PK, receptor occupancy and pharmacodynamic during the Q3W administration, it was deemed necessary to study more frequent dosing. With a country specific addendum, Q2W and Q1W dosing intervals are implemented into Part II. These are evaluated as separate Part II expansion cohorts.

[figure not shown]

Figure 1. Study design

5 Study variables

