Regarding Part II, the first three subjects recruited to the unique cohort are included in the DLT evaluable population. The amount is expanded to six subjects if there is one DLT event in the first three subjects. The following cohorts are investigated: Q3W cohorts at dose levels that have not previously been tested in Part I, Q2W cohorts at each new dose level and Q1W cohorts at each new dose level. DLT assessment period in Part II is 4 weeks from the first dose of FP-1305.

Efficacy evaluable population: Includes all subjects who have received at least one dose of FP-1305 for the first time and has tumour imaging conducted at the baseline, and at least once during the treatment or progress or die due to their disease before the first tumour imaging post FP-1305 administration. This formulates the Full Analysis Set for Efficacy (FAS-E).

In the FAS populations also Part I subjects will be included.

9 General statistical considerations

Summary statistics will include at least the number of subjects, mean, standard deviation, median, minimum and maximum for continuous variables, and frequencies and percentages for categorical variables. All data collected will be listed by subject.

In Part II, the disease group or dosing cohorts of 10 subjects will be presented separately as also the Simon's design rule will be applied separately for each cohort. In addition, the cohorts using originally recommended dosing regimen for Part II, Q3W (1.0 mg for all cohorts and 0.3 mg/kg and 3.0 mg/kg for colorectal adenocarcinoma), will form a population (originally enrolled part II cohorts). Also, a pooled population of Part I subjects (n=30) and Part II originally enrolled subjects (n=120) will be used for survival endpoints. The total number of subjects in this dataset is n=148 as there were 2 part I subjects (colorectal adenocarcinoma 0.3 mg/kg) included in Part II.

In the statistical analyses a p-value less than 0.05 will be considered as an indication of statistical significance. If not stated otherwise, all tests will be performed as two-sided tests and two-sided 95% confidence intervals will be produced. Missing values will not be imputed in the analyses.

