9.3 Examination of subgroups

All analyses will be presented by tumor type cohorts. In addition, within colorectal adenocarcinoma, results will be presented by dose and by dosing frequency. Furthermore, some disease group cohorts can be combined for subgroup analyses:

- disease cohorts in which there are subjects who have at least SD for overall response evaluation
- cutaneous melanoma, cholangiocarcinoma, gastric adenocarcinoma and hepatocellular cancer which have subjects with a long duration of disease control
- cutaneous melanoma, cholangiocarcinoma and gastric adenocarcinoma cohorts (30 subjects) will be used as a subgroup of investigating the possible predictive markers of clinical benefit, in addition to whole subject population

Subgroup presentations to be done will be indicated in the sections below.

10 Demographic and other baseline characteristics

Number of subjects enrolled into the study at screening and the reasons for screening failures will be summarized. The number of subjects entering and completing the study will be summarized. All subjects discontinuing the study will be summarized together with the reason(s) for discontinuation and time of discontinuation (visit/cycle).

Demographic and baseline characteristics will be summarized by disease group using descriptive statistics. Following variables will be analysed.

- Gender
- Age at entry
- Race
- Weight
- Pregnancy test (females of child-bearing potential)
- Tumour information and other baseline disease characteristics

Medical history, prior and concomitant medications/therapies will be presented by frequency and subject count-based tables according to MedDRA/WHO Anatomical Therapeutic Chemical (ATC) classification.

A prior medication is a medication with end date strictly before administration of first dose of IMP.

11 Extent of exposure and compliance

Treatment exposure (number of cycles), study duration and treatment compliance will be summarised for all subjects and by disease group cohorts using descriptive statistics.

12 Outcome variables

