20.1 Table and figure plan

List of planned tables:

Section 14.1
Disposition of subjects
Demographics and baseline characteristics
Medical history
Prior medications
Concomitant medications - other than chemotherapy or concomitant procedures
Concomitant medications related to chemotherapy or concomitant procedures
Extent of exposure and compliance
Section 14.2.1
Best response at any timepoint for Target-lesion, non-Target lesion and Overall response
Response by cycle
Simon's two-stage evaluation of stage one
Other response related information
Section 14.2.2
Monocytes CLEVER-1 positivity
S-CLEVER-1 and its occupancy by FP-1305
Serum concentration of FP-1305
Anti-human FP-1305 antibodies
Section 14.2.3
Lymphocyte subsets
B-cells

Regulatory T-cells
Circulating cytokines and chemokines
Change in LDH, LDL, CRP
Change in OxLDL
Change in CA-125
Change in CA19-9
Change in CEA
Change in CA-15-3
Change in AFP
Response with the immune cell profile by DCR and in total
The level of circulating cytokines and chemokines by DCR and in total
CLEVER-1 on circulating monocytes by DCR and in total
IHC parameters
Clever-1 and PD-L1 staining parameters
Overall survival
Overall survival (Cox regression)
Overall survival (Kaplan-Meier)
Progression free survival
Progression free survival (Cox regression)
Progression free survival (Kaplan-Meier)
Duration of response
Association of tumor responses to survival (Landmark analysis)
Length of latest prior treatment line for the cancer impact on survival
Length of latest prior treatment line compared to length of treatment in study
Subgroup evaluations
ECOG
Section 14.3.1
Overall summary of TEAEs
TEAEs by system organ class and preferred term
TEAEs by system organ class and preferred term by causality
TEAEs by system organ class and preferred term by severity
Serious TEAEs by system organ class and preferred term
TEAEs leading to discontinuation of study drug by system organ class and preferred term
Overall summary of pooled (Part 1 and Part 2) TEAEs by dose
Section 14.3.3
Hematology
Hematology shift
Chemistry
Chemistry shift
Urinalysis
Other lab parameters

Section 14.3.3

Vital signs
ECG
ECG maximum change
ECG abnormal findings
Physical examination

List of planned figures:

Section 14.2.4

Serum concentration of FP-1305
Lymphocyte subsets
B-cells
Regulatory T-cells
Macrophage HLA expression
Myeloid derived suppressor cell populations in circulation
Immune cell profile by DCR status and overall

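### The one adverse-event output that the Part II SAP lists by dose pools tumour types, so for 0.3, 1.0 and 3.0 mg/kg it mixes dose with tumour type

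*SAP*

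**What the plan says.** Protocol section 4 sets Part II cohorts at "10 at each dose level with random allocation within the same dosing schema". SAP Part II section 4 gives the Q3W doses of the original cohorts as "1 mg/kg for all cohorts and 0.3 mg/kg, 1.0 mg/kg and 3.0 mg/kg for colorectal adenocarcinoma cohort", so among these only colorectal cancer has more than one dose.

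For safety, SAP Part II 14.1 tabulates TEAEs, serious events and events leading to discontinuation by disease group. It then adds one display by dose: "Pooled AE data from Part I and Part II will be tabulated by dose". The table list in 20.1 has one matching entry: "Overall summary of pooled (Part 1 and Part 2) TEAEs by dose". No tumour-type stratum is named in either place.

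Three other passages bear on the point:

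- Protocol 15.3.4.5 asks for adverse events to be evaluated by dose level and by disease group.
- SAP Part II 9.3 states that "within colorectal adenocarcinoma, results will be presented by dose and by dosing frequency", and adds that the subgroup presentations will be identified in later sections.
- Protocol 11.3 states: "Disease progression will be recorded as an AE/SAE in this study".

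**The concern.** Safety and tolerability is a primary outcome of Part II. A reader who wants to know whether adverse events change with dose will turn to the table titled by dose. Across 0.3, 1.0 and 3.0 mg/kg, that table largely compares colorectal cancer with a mixture dominated by nine other tumour types. Because disease progression counts as an adverse event, TEAE and serious-event rates can plausibly differ by tumour type whatever the dose. The table could then show a dose effect that does not exist or conceal one that does. The colorectal groups, where dose was to be allocated at random, would give a cleaner contrast, but no adverse-event table for them is listed.

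**Working it through.** **Inputs from the documents.** The reported Part II set is 12 cohorts of 10 = 120 (SAP Part II section 2). Ten tumour types received 1.0 mg/kg, and colorectal cancer also received 0.3 and 3.0 mg/kg (section 4). Part I had 30 subjects at 5 dose levels (SAP Part I section 12). Two Part I colorectal subjects at 0.3 mg/kg are counted in Part II (SAP Part II section 9).

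**The plan's own count.** 30 + 120 − 2 = 148, which matches the pooled total in SAP Part II section 9.

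**Tumour mix by dose, original Part II cohorts**

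| Dose (mg/kg) | n | Colorectal | Other | Share other |
|---|---|---|---|---|
| 0.3 | 10 | 10 | 0 | 0 |
| 1.0 | 100 | 10 | 90 | 0.90 |
| 3.0 | 10 | 10 | 0 | 0 |

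**Spurious difference when dose has no effect.** Let s be the share of non-colorectal subjects at a dose, and let Δ be the TEAE rate in other tumours minus the rate in colorectal cancer. The crude difference between 1.0 mg/kg and a comparator dose is (s at 1.0 − s at comparator) × Δ.

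- Part II only: (0.90 − 0) × Δ = 0.9Δ. With assumed rates of 30% in colorectal cancer and 50% elsewhere, the table shows 30%, 48% and 30% at 0.3, 1.0 and 3.0 mg/kg, a gap of 18 points. Reversing the two rates reverses the sign.

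**A real effect can also vanish.** Suppose the colorectal rate is 20% at 1.0 and 40% at 3.0 mg/kg, and other tumours at 1.0 mg/kg have 42.2%. The crude rate at 1.0 mg/kg is 0.1 × 20 + 0.9 × 42.2 = 40%, equal to the rate at 3.0 mg/kg.

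**Adding Part I.** The split by dose and tumour type is not given. Assume 6 subjects per level (30/5), with the tumour mix otherwise unknown. Then n is 8 + 6 = 14, 100 + 6 = 106 and 10 + 6 = 16 at 0.3, 1.0 and 3.0 mg/kg. Non-colorectal counts are 0–4, 90–96 and 0–6. With Δ = 20 points:

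- 1.0 v 0.3 mg/kg: smallest (90/106 − 4/14) × 20 = 0.563 × 20 = 11 points; largest (96/106 − 0) × 20 = 0.906 × 20 = 18 points.
- 1.0 v 3.0 mg/kg: smallest (90/106 − 6/16) × 20 = 0.474 × 20 = 9 points; largest 18 points.

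With 2 to 10 Part I subjects at each of 1.0 and 3.0 mg/kg and any tumour mix, the gap in colorectal share between those doses stays between 0.32 and 0.91, which is 6 to 18 points for the same Δ.

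**Precision of the colorectal contrast.** The 95% Wald half-width for 10 v 10 is 1.96 × √(2p(1 − p)/10): ±35 points at p = 20% and ±44 points at p = 50%. Leaving out the two Part I subjects makes contrasts with 0.3 mg/kg 8 v 10: 1.96 × √(p(1 − p)(1/8 + 1/10)) gives ±37 and ±46 points.

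**The case against.** The strongest reply is that the plan already provides the unconfounded view. SAP Part II 9.3 promises colorectal results by dose without limiting this to efficacy, section 9 presents dosing cohorts of 10 separately, and section 16 declares no major deviation from a protocol that asks for adverse events by dose level and disease group. The titles in 20.1 are also shorthand: other TEAE entries omit the disease-group breakdown that 14.1 requires. This stands in part. A reader might infer that no colorectal by-dose safety display is intended, and the documents do not support that. But 9.3 leaves the choice of presentations to later sections, and 14.1 names none for adverse events by dose within colorectal cancer. The protocol sentence could be read as two one-way tabulations, but neither would show dose within tumour type.

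A second reply is that nothing is decided from the pooled table. This stands. Protocol section 4 ties progression to Part III to efficacy: "Cohorts with best efficacy signal at any dose level may be advanced to Part III". Tolerability of new Part II doses rests on 28-day DLTs, and 0.3 to 3.0 mg/kg were Part I levels with no DLT among 30 subjects. The harm is a misleading reading of reported safety, not a wrong trigger.

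A third reply is that the rate gaps are assumed. That is also true. The protocol's survival figures by tumour type come from differing settings and do not measure adverse-event rates in this late-line population. Causality tabulation will also help to separate progression events.

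**Conclusion.** The point holds as a gap in the listed adverse-event outputs, worth closing because it costs little. The imbalance in tumour mix follows from the plan's own counts. The 18 points, and the 9 to 18 points with Part I added, are illustrations: they assume a 20-point tumour-type gap, one common rate for all non-colorectal tumours, the same rates in Parts I and II and, for the range, 6 Part I subjects per level. If the later 3.0 mg melanoma and gastric cohorts are pooled too, the colorectal share at 3.0 in Part II falls from 10/10 to 10/30, which reduces the imbalance against 10/100 at 1.0 mg/kg but does not remove it.

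A reader might go further and infer that the plan owes a formal efficacy comparison between doses, or that its power of 0.80 is meant to cover one. Neither is supported. SAP Part II section 9 says "Simon's design rule will be applied separately for each cohort", 12.1 gives a 90% confidence interval for each cohort and dosing regimen, the analyses are declared exploratory, and Protocol 15.7 states the power only for a cohort tested against 5%. An efficacy trend test or a revised power statement would be a matter of preference.

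**What to change.** In SAP Part II 14.1 and 20.1:

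1. Split the pooled TEAE-by-dose table by tumour type (at least colorectal v other) and by study part, and label it as a non-randomised comparison.
2. List a TEAE table by dose within colorectal Q3W subjects randomly allocated in Part II, leaving out the two carried over from Part I. Show any, Grade 3 or higher, and serious TEAEs, each with and without disease-progression events. Give descriptive between-dose differences with confidence intervals, labelled exploratory.

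This needs SAP wording and a few tables from data already collected, with no new subjects or procedures. The intervals will be wide, so the second table gives an estimate free of the tumour-type imbalance, not a powered test.

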14.2 Laboratory safety variables

Laboratory safety variables comprise of hematology and chemistry parameters. Descriptive statistics will be provided by time point and disease group. Change from baseline (absolute and percentage) will be included in the reporting. Visual illustrations (by subject and by disease group) will be provided. In addition, shift tables (within, below and above the normal range) will be provided for each parameter in relation to the maximum change from baseline from D0 over the complete follow-up period. Some of the laboratory safety parameters can be used also as part of the biomarker analysis.

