5.1 Inclusion and Exclusion Criteria

5.1.1 Inclusion Criteria

Subjects must meet all of the following inclusion criteria to be eligible for participation in the clinical trial:

- 1) Written Informed Consent
- 2) Aged \geq 18 years male or female
- 3) Tumour sample should be collected during screening period. If a recent tumour biopsy obtained within six months before the date of consent is available (or older, as agreed on a case by case basis with the sponsor), that may be used. At the discretion of the sponsor, the tumour sample may be optional for certain subjects in Part III
- 4) Life expectancy $>$ 12 weeks
- 5) Histologically confirmed advanced (inoperable or metastatic) malignancies in which (according to the view of the investigator) no curative, effective or suitable treatment options exist.
 - Hepatocellular carcinoma
 - Gallbladder cancer or intra- or extrahepatic cholangiocarcinoma
 - Colorectal adenocarcinoma
 - Serous poorly differentiated (Grade 3) ovarian adenocarcinoma or undifferentiated ovarian cancer
 - Pancreatic ductal adenocarcinoma
 - Immunotherapy (IO) resistant cutaneous melanoma (progression during programmed cell death protein-1 (PD-1)/programmed cell death ligand-1 (PD-L1) or CTLA-4 antibody therapy)
 - Uveal melanoma in Parts II and III
 - Gastric adenocarcinoma (including adenocarcinoma of the distal esophagus / GE junction) in Parts II and III
 - ER+ breast cancer in Parts II and III
 - Anaplastic thyroid cancer in Parts II and III
- 6) Eastern Cooperative Oncology Group (ECOG) performance status 0 or 1
- 7) Measurable disease in Parts II and III
- 8) Adequate bone marrow, liver and kidney function defined as

Blood white blood cell \geq lower limit of normal

Blood neutrophil count $\geq 1 \times 10^9/L$

Blood platelet count $\geq 100 \times 10^9/L$, for HCC $\geq 50 \times 10^9/L$

Blood haemoglobin $\geq 9.0 \text{ g/dL}$

Creatinine clearance $> 40 \text{ mL/min}$ calculated by Cockcroft-Gault formula

AST $\leq 3 \times \text{ULN}$ ($\leq 5 \times \text{ULN}$ when HCC or hepatic metastases are present)

ALT $\leq 3 \times \text{ULN}$ ($\leq 5 \times \text{ULN}$ when HCC or hepatic metastases present)

Bilirubin $\leq 1.5 \times \text{ULN}$

Albumin $\geq 3.0 \text{ g/dL}$

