15.3 Laboratory safety variables

Part of the laboratory safety measurements will be used for dose response evaluation and reported along that. For completeness, the descriptive statistics of all safety parameters will be reported as a part of safety data also. Safety labs collected are listed in the schedule of assessments for Part 1 (see appendix). Aggregated data (mean and median) from each dose level will be presented using descriptive statistics. In addition, shift tables (within, below and above the normal range) will be provided for each parameter in relation to the maximum change from baseline from D0 over the complete 30-day follow-up period.

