The following variables will be evaluated for Part II of the study:

The demographic and baseline variables

Gender, age at entry, race, weight, height, medical history, concomitant medications/therapies (including prior cancer therapies), CMV infection status and pregnancy test (females of child-bearing potential), ECOG performance status, baseline tumour imaging results and HIV serology.

Part II

Primary outcome measure

- Safety and tolerability will be defined by physical examination, adverse events and by safety laboratory tests. Adverse events are collected, graded and reported according to the NCI-CTCAE version 5.0. MedDRA terminology will be used to classify, record, manage, and analyse the data. Tolerability of new dose(s) will be determined based on the occurrence/non-occurrence of dose limiting toxicity (DLT) during 28 days following the first dose of FP-1305 in subjects evaluable for DLT assessment in Part II.
- The response (ORR, CBR, and irORR separately) to the treatment will be determined by tumour imaging according to RECIST 1.1 based on images obtained by Cycle 7. Results from each tumour type, dose level and dosing frequency will be reported separately.

Secondary outcome measures

- The PK profile of a single dose (during Cycle 1) and repeated doses (during Cycles 2-5) of FP-1305 will be determined by repeated measurements of the drug concentration in the circulation. Peak concentration (C_{\max}), trough concentration (C_{\min}), area under the serum concentration versus time curve (AUC), clearance, volume of distribution, and terminal halflife ($t_{1/2}$) for each dose level will be determined. Results from each tumour type will be reported separately.
- Immunogenicity will be evaluated by assessing anti-drug antibodies in the circulation periodically during treatment and follow-up. Results from each tumour type will be reported separately.
- Potential predictive genetic, cellular and other markers will be associated with FP-1305 clinical activity as determined by ORR, CBR and irORR. This includes but is not limited to the correlation of response and immune cell profile, cytokine/chemokine profile and the proportion of CLEVER-1-positive monocytes, CD4, CD8, their ratio and regulatory T-cells in the circulation and in tumour specimens prior to treatment and in circulation during the first cycle of treatment.

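### The laboratory shift tables cannot show further worsening of a parameter already abnormal at baseline, and can miss a transient fall

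*SAP*

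**What the plan says.** The Part II SAP, Section 14.2, plans descriptive statistics and change from baseline by time point and disease group, then adds that "shift tables (within, below and above the normal range) will be provided for each parameter in relation to the maximum change from baseline", counted from D0 over the whole follow-up. The table plan (Section 20.1) has one shift table for haematology and one for chemistry. Neither place says whether the maximum is the largest signed change or the largest absolute change.

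The Part I SAP, Section 15.3, has the same three categories, read "in relation to the maximum change from baseline from D0 over the complete 30-day follow-up period". Its table plan (Section 21.2) also lists tables of haematology and chemistry abnormalities by visit and dose (Tables 14.3.3.3 and 14.3.3.7). The Part II plan has no counterpart.

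In Part II, laboratory safety belongs to the primary outcome (Part II SAP, Section 5): "Safety and tolerability will be defined by physical examination, adverse events and by safety laboratory tests".

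Protocol Section 5.1.1 admits subjects outside the normal range. AST and ALT may be up to 3 × ULN, or 5 × ULN "when HCC or hepatic metastases are present" (AST; the ALT criterion matches). Bilirubin may be up to 1.5 × ULN, haemoglobin may be as low as 9.0 g/dL, neutrophils as low as 1 × 10⁹/L, and platelets as low as 100 × 10⁹/L (50 in HCC).

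**The concern.** A shift table should show how many subjects moved to a worse laboratory state on treatment. This one has no category beyond abnormal, so it has nowhere to put a subject who enters abnormal and gets worse. Eligibility expressly admits such subjects, with the widest liver-enzyme limits for those with HCC or hepatic metastases.

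The protocol judges them on finer scales. The DLT definition (Section 4.1) and the definition of liver injury as an adverse event of special interest (Section 11.5) use CTCAE grade together with bilirubin relative to baseline where baseline was abnormal. Section 8.9.2.4 grades transaminases as multiples of baseline in the same situation. A three-category table can express none of this.

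Section 11.5 also reports four subjects with hepatic involvement, described under differing adverse event terms, with some events graded life-threatening. Differing terms can split one liver signal across several rows of an adverse event table. A graded laboratory summary would keep it together.

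The single reading per subject is a second weakness. A low count at one visit and a recovery or rebound at another compete for the same cell.

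**Working it through.** The plan gives no figure to reproduce on this point, so the stated rule was applied to worked cases.

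**Rule.** Let b be the baseline and v the post-baseline values. The signed reading selects the v with the largest v − b, which is the highest value. The absolute reading selects the v with the largest |v − b|. The table cell is category(b) → category(selected v).

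**Inputs.** Entry limits are from Protocol Section 5.1.1. The Grade 2 transaminase rule for an abnormal baseline, more than 3.0 and up to 5.0 × baseline, is from Section 8.9.2.4. The normal ranges are assumed, because the documents give none: platelets 150–400 and neutrophils 1.5–7.5 × 10⁹/L. The ALT cases need only the ULN.

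**1. Abnormal at baseline.** If b is above 1 × ULN, any value above b is too, so a rise can only read above → above. Each case below runs from baseline to the peak and back (ALT in × ULN):

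| Baseline | Peak 1.1 × b (below Grade 2) | Peak 4 × b (Grade 2) | Peak 6 × b (above Grade 2) |
|---|---|---|---|
| 1.5 | 1.65 | 6 | 9 |
| 2 | 2.2 | 8 | 12 |
| 3 | 3.3 | 12 | 18 |
| 5 | 5.5 | 20 | 30 |

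All 12 give above → above under both readings. Low baselines behave the same way: platelets 110 → 20 → 115 and neutrophils 1.2 → 0.4 → 1.3 both read below → below.

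**2. Normal at baseline, transient fall** (× 10⁹/L):

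| Path | Changes | Signed reading | Absolute reading |
|---|---|---|---|
| Platelets 250, 40, 260 | −210, +10 | within → within | within → below |
| Platelets 250, 40, 480 | −210, +230 | within → above | within → above |
| Platelets 250, 140, 370 | −110, +120 | within → within | within → within |
| Neutrophils 4.5, 0.9, 9.5 | −3.6, +5.0 | within → above | within → above |
| Neutrophils 4, 0.4, 4.2 | −3.6, +0.2 | within → within | within → below |
| Neutrophils 4.5, 0.9, 1.2 | −3.6, −3.3 | within → below | within → below |

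Under the signed reading a fall is lost once any other post-baseline value is back within or above normal. Under the absolute reading it is lost only if a rise exceeds the fall. In rows 1 and 5 the undefined word alone decides the cell. The last row shows that a sustained fall appears under either reading.

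**3. What would recover each case.** Reading the lowest and highest values separately turns platelets 250, 40, 260 and 250, 40, 480 into within → below in the low direction. It does nothing for ALT 2 → 12 × ULN, which stays above → above. That case needs grades or multiples of baseline.

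**The case against.** The strongest reply is that the shift tables are one output among several.

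- Section 14.2 of the Part II SAP also plans absolute and percentage change and by-subject plots, and Section 9 requires minimum and maximum. ALT rising from 2 to 20 × ULN would appear as a 900% change ((20 − 2)/2), and a neutrophil count of 0.9 could appear as a visit minimum.
- Protocol Section 11.3 makes a pre-existing abnormality an adverse event once it worsens by one CTC grade. SAP Section 14.1 tabulates events by severity and lists those of special interest. The laboratory values are listed, and cohorts hold only 10 subjects.
- Dose escalation rests on DLTs and Part III expansion on CBR. SAP Section 16 calls the analyses exploratory.

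All this stands and limits the point, but does not remove it. Section 11.3 leaves laboratory adverse events to the investigator's view of clinical significance, and exempts findings associated with the disease unless more severe than expected. That discretion is likely to be widest in HCC and liver metastases. Visit summaries do not link one subject's baseline to that subject's worst value, and listings summarise nothing. Section 14.2 promises plots, but the planned figure list has none for haematology or chemistry.

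A reader might infer more than the documents support:

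- **That the whole safety analysis is blind to liver worsening.** The outputs above can still reveal it.
- **That low counts can never appear under the signed reading.** Sustained falls do.
- **That a large share of subjects can show no hepatic shift at all.** The documents give no baseline distribution, and the tables run parameter by parameter. A subject with raised ALT and normal bilirubin can still show a bilirubin shift.
- **That Part I is equally affected.** Its by-visit abnormality tables partly offset the same rule.

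**Conclusion.** The point holds for the Part II shift tables. For a parameter already abnormal at entry, further worsening in the same direction cannot appear in them, whatever its size. This follows from the three categories and the entry limits alone. A transient fall can also be missed, and how often depends on a term the SAP leaves undefined. The examples rest on assumed normal ranges for platelets and neutrophils.

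The number of subjects affected cannot be estimated from the documents. No dosing or expansion rule depends on these tables. Still, no planned Part II table summarises baseline against worst grade, in a trial where laboratory tests are part of the primary outcome and liver injury is of special interest. The tables should be changed; the weakness does not undermine the trial's design. In Part I the same rule is a lesser problem.

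**What to change.** In Part II SAP Section 14.2 and the table plan, replace the shift tables with baseline CTCAE v5.0 grade (or ULN/LLN category) against worst post-baseline grade. Use all scheduled and unscheduled values, treat the low and high directions separately, and present by disease group and dose. Where the baseline is abnormal, also tabulate the worst value as a multiple of baseline. Add a table or plot of peak ALT/AST against peak bilirubin, using the thresholds already in Protocol Section 11.5. Define the baseline measurement too: the SAP counts from D0, whereas the schedule starts at Day 1 and allows most pre-dose samples up to three days earlier.

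If the Part I outputs are re-run, the same shift rule can be applied there. The cost is programming only. CTCAE v5.0 is already the protocol's grading standard, the laboratory values are already collected, and no clinical rule changes.
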